9.5 Halting Rules

The study will be halted if the following occurs:

- One or more participants have laryngospasm, bronchospasm, or anaphylaxis associated with study procedure and occurring within 72 hours post study procedure;
- Any SAE associated with study product or procedure;
- Two or more participants experience the same or similar severe or life-threatening AE judged to be associated with study procedure.

9.6 Safety Oversight

Safety oversight is the responsibility of the Independent Safety Monitor (ISM). The ISM will be approved by DMID in accordance with DMID guidelines. Serious and severe adverse events will be reported to the ISM and DMID. The DMID Medical Monitor has the authority to stop study enrollment, vaccinations and procedures if AEs are reported that meet halting criteria.

9.6.1 Independent Safety Monitor (ISM)

An ISM at the site will review adverse events in a timely fashion and ensure that appropriate management is initiated and completed at the site. The ISM will have direct contact with the Principal Investigator and follow all events on an on-going basis. Any issues or questions will be directed to the DMID CPM.

10 CLINICAL MONITORING

Purpose: to protect the rights and well-being of human subjects in this study; to ensure that data are accurate, complete and verifiable from source documents; to ensure that conduct is in compliance with the currently approved protocol/amendments, with Good Clinical Practice, and with regulatory requirements.

10.1 Site Monitoring Plan

Site monitoring will be conducted using the DMID tools provided to ensure that human subject protection, study procedures, laboratory procedures, and data collection processes are of high quality and meet sponsor, GCP/ICH, and regulatory guidelines, and that the study is conducted in accordance with the protocol and sponsor standard operating procedures. DMID, the sponsoring agency, or its designee will conduct site-monitoring visits as defined in the CQMP.

A protocol-specific Clinical Quality Management Plan (CQMP) has been approved for this study by DMID. The Quality Assurance (QA) plan will be implemented by a weekly review of source documents by the CRC to determine adherence to protocol requirements. The Quality Control (QC) plan will be implemented by daily observation and documentation of the site's work processes by study staff, to ensure that accepted procedures are followed.

Site visits may be made at standard intervals as defined by DMID and may be made more frequently as directed by DMID. Monitoring visits will include, but are not limited to, review of regulatory files, sample tracking log, CRFs, informed consent forms, medical and laboratory reports, and protocol compliance. Study monitors will meet with investigators to discuss any problems and actions to be taken and document visit findings and discussions. Emory University IRB and other regulatory agencies may conduct study monitoring visits.

11 STATISTICAL CONSIDERATIONS

For this study we will assess immunologic responses in the periphery (blood) and centrally (bone marrow). These responses contain a variety of immunologic assays with different types of response output. Hence our primary data analytic strategy will be the use of longitudinal data analysis methods to determine the temporal course of a given response measurement and factors associated with heterogeneity in that temporal course. Study outcomes will be measured using numerical data from laboratory assays including flow cytometry and ELISPOT assays. A detailed data management system will utilize general linear mixed models for continuous responses to assess differences among time points.

11.1 Study Hypothesis

To investigate the longevity of humoral immunity to influenza virus in humans. Our overarching hypothesis is that an understanding of how long-term humoral immunity to influenza virus is generated and maintained is essential for the development of a “universal” vaccine against influenza virus. This aim will be accomplished by measuring the total influenza-specific and hemagglutinin stem-specific bone marrow plasma cells, memory B-cells, and serum antibody levels over extended periods following vaccination.

11.2 Sample Size Considerations

A major goal our study is to understand the longevity of plasma cell responses directed against different determinants in the influenza vaccine. Our preliminary data has suggested that plasma cell clonal responses against conserved epitopes may be smaller in number and less prone to persist compared to responses against epitopes which are unique to the particular hemagglutinin strains used in the current year's vaccine. Our deep sequencing data suggests that after one year the frequency of the average vaccine-induced clone in the bone marrow is approximately 33% of the frequency observed at one month. However, there is a large variability in this maintenance (standard deviation of 44%). The small number of cross-reactive clones we have tracked so far have been undetectable after one year, suggesting that their maintenance is substantially lower than the average clone. We wish to be 80% confident in being able to detect whether the maintenance of these cross-reactive clones is at least 3-fold lower than for the average clone (i.e. 11% maintenance vs. 33%) with a P-value less than 0.05. This will require the longitudinal tracking of at least 25 broadly cross reactive plasma cell clones in our patient cohort. Our initial data suggests that we should be able to identify a single broadly cross-reactive clonotype in approximately 50% of our donors, meaning that a sample size of 50 donors will be required to follow 25 cross-reactive clonotypes. With our planned sample size of 55 donors, this allows for a potential dropout rate of 10%.

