needed to secure the appropriate approvals and clearance to bring research participants back for their missed visits. As such, we would like to request that the missed visit windows for the Day 28 and Day 90 visits be extended for a maximum of up to 180 days, to ensure that ample time is available to bring participants back for their missed visits. Enrollment for this study ended on March 31, 2020.

Subjects will be offered the opportunity to participate in the study for up to 3 consecutive years provided eligibility criteria is met each year. Subjects who elect to continue in the study after first year of participation will be rescreened to verify continued eligibility and re-consented prior to subsequent participation. Re-enrolling subjects will receive new subject identifiers and will count towards the total enrollment number for subsequent years of participation. A separate subject record will be maintained each year a subject re-enrolls in the study.

Schematic of Study Design:

| Subjects enrolled in study | Years study performed | Number of subjects per year (study total) | Blood or Bone Marrow samples (days post-influenza vaccination) |
|------------------------------|-----------------------|--|---|
| Healthy adults (18-49 years) | Years 1-4 | Years 1-3: 15/year Year 4: 10 (Total: 55) | Blood volume 64ml per visit (320 ml total)– Day: 0, 7, 14, 28, 90, 365* Bone marrow aspirate volume 30 ml per visit (90ml total)– Day: 0, 28, 365* |

* Subjects that consent to be in the study for subsequent years, the “Day 0” of the second and third years will constitute “day 365” and “day 730” with respect to the first year of participation.

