11.4 Final Analysis Plan

We will use the unpaired Student's t-test to compare the frequencies of strain-specific and broadly cross-reactive clonotypes in the marrow after one year as expressed as a percentage of their frequencies at one month post vaccination. We will also work to develop a multi-phase exponential decay model for plasma cell persistence in the blood and bone marrow over time. We will use ANOVA to evaluate the contributions of antibody specificity (head vs. stem specific; broadly reactive versus strain specific reactivity), affinity for antigen, and level of hypermutation on the observed exponential decay constants of individual clones in each decline phase that we identify through our modeling. This work will be performed in collaboration with the Emory/UGA CEIRS Data Management Team headed by [name] using the approved Data Management Plan for this contract.

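### Section 11.2 claims 80% power from 25 cross-reactive clones, but its stated inputs do not give that power for the unpaired t-test planned in 11.4

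*Combined protocol and SAP*

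**What the plan says.** Section 11.2 holds the only sample-size justification. It takes from preliminary sequencing that the average vaccine-induced clone stands, at one year, at about 33% of its one-month frequency in the marrow. On spread it says "However, there is a large variability in this maintenance (standard deviation of 44" (percent). The target is: "We wish to be 80% confident in being able to detect whether the maintenance of these cross-reactive clones is at least 3-fold lower". In figures, this means 11% for cross-reactive clones against 33% for the comparator, tested at the 0.05 level. From this it concludes "This will require the longitudinal tracking of at least 25 broadly cross reactive plasma cell clones in our patient cohort". At about one such clone in half of donors, 25 clones become 50 donors, and the section closes with "With our planned sample size of 55 donors, this allows for a potential dropout rate of 10" (percent).

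Section 11.4 names the analysis: "We will use the unpaired Student's t-test to compare the frequencies of strain-specific and broadly cross-reactive clonotypes", each expressed as one-year frequency relative to one month.

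Neither section says whether the test is one- or two-sided. Section 11.2 gives no expected number of comparator clones and no SD specific to cross-reactive clones. The comparator is the average clone in 11.2 and strain-specific clones in 11.4.

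**The concern.** An unpaired t-test carries sampling error from both groups, so its power depends on both group sizes and both SDs. Section 11.2 sizes one group only and gives one SD, which describes the average clone. The 25 is also small for a standardized difference of 0.5.

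The 55 donors rest on this calculation. If the real power is well below 80%, a non-significant result could be over-read as evidence that cross-reactive clones persist as well as others. The stake is limited to this test: clonotype tracking is an exploratory outcome (3.2.3), and the primary outcomes in 3.2.1 do not depend on it.

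**Working it through.** **Inputs from 11.2:** difference 33 − 11 = 22 points; SD 44 points; power 80%; alpha 0.05; 25 cross-reactive clones. Standardized difference d = 22/44 = 0.5. **From 11.4:** unpaired two-sample t-test. **Not stated, so varied:** sidedness, number of comparator clones (n2), SD of cross-reactive clones.

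**Reproducing the 25.** With variance from one group only, n = (z_alpha + z_power)² / d².
- One-sided: (1.645 + 0.842)² / 0.25 = 24.7, so 25. This matches.
- Two-sided: 31.4, so 32.

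The one-sided result fits either a fixed 33% reference or equal groups with zero SD among cross-reactive clones. The documents do not say which, if either, was used.

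**The planned test, equal groups, SD 44 in both.** n per group = 2(z_alpha + z_power)² / d² = 49.5 one-sided or 62.8 two-sided; with the t distribution, 51 and 64.

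**Power with 25 cross-reactive clones, SD 44 in both groups.** Noncentral t with 25 + n2 − 2 degrees of freedom and noncentrality 22 / [44·√(1/25 + 1/n2)]; normal data, independent clones.

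| n2 | Two-sided power | One-sided power | Detectable difference at 80%, two-sided | One-sided |
|---|---|---|---|---|
| 25 | 41% | 54% | 35.6 | 31.4 |
| 50 | 52% | 65% | 30.6 | 27.1 |
| 100 | 60% | 72% | 27.8 | 24.6 |
| 250 | 66% | 77% | 25.9 | 23.0 |
| unlimited | 70% | 80% | 24.7 | 21.9 |

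Two-sided, no number of comparators reaches 80%. One-sided, power is 79.9% at 2,000 comparators and passes 80% only beyond that. With 25 comparators the two-sided detectable difference (35.6 points) exceeds the whole 33-point distance to zero maintenance.

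**Smaller SD in cross-reactive clones** (assumed values, comparator SD 44, pooled t-test, simulated normal data, n2 = 25/50/100/250):
- SD 30: 53/62/68/74% two-sided; 65/75/81/86% one-sided.
- SD 14.7 (one third of 44): 64/71/79/87% two-sided; 76/84/91/96% one-sided.
- SD 0: 69/76/84/95% two-sided; 79/87/95/99.5% one-sided.

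So 80% can be reached, but only with inputs the plan does not give. With unequal SDs the pooled test is also a poor choice. At 14.7 vs 44 with 50 comparators, Welch's test has 88% two-sided power against 71% pooled, and the pooled test's true type I error falls to 1.1%.

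**Clone yield.** At 50% per donor, 25 is the expected number from 50 distinct donors, not a minimum. The binomial chance of at least 25 is 56% with 50 donors, 79% with 55 and 28% with 45 (an assumed figure). The number of distinct donors matters because "Re-enrolling subjects will receive new subject identifiers and will count towards the total enrollment number for subsequent years of participation". With only 20 cross-reactive clones, two-sided power at SD 44 is 37/46/53/57% for n2 = 25/50/100/250.

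**Clones within donors.** Independence is favourable. If 250 strain-specific clones came as 5 from each of 50 donors with intraclass correlation 0.3 (assumed), they would count as 250 / (1 + 4 × 0.3) = 114, and two-sided power would be 61% rather than 66%.

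**The case against.** The strongest objection is that SD 44 in both groups under a normal model is unrealistic. Maintenance cannot be negative, yet a normal distribution with mean 11 and SD 44 puts 40% of clones below zero. Section 11.2 itself reports: "The small number of cross-reactive clones we have tracked so far have been undetectable after one year", which points to a smaller spread. With non-negative (gamma) data of the same means and SDs, the pooled test at SD 44 in both groups has 59/66/70/74% two-sided power and 67/74/78/81% one-sided power at 25/50/100/250 comparators. At SD 14.7 vs 44 it has 73/81/87/90% two-sided.

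This stands in part. The exact percentages depend on the model, and the need for more than 2,000 comparators one-sided belongs to normal theory; in the gamma model about 250 suffice. But two-sided power at the only stated SD stays below 80% in both models up to 250 comparators. The cases that reach 80% need a smaller SD or a one-sided test with many comparators, neither of which is in the plan.

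Two further points are fair. Section 11.2 expects responses to conserved epitopes to be fewer than strain-specific ones, so 25 against 25 is the least likely case and the low end of the range. And enrolment ended on March 31, 2020, the outcome is exploratory, and 11.4 also plans decay modelling and ANOVA on clone specificity. These limit the consequence but do not support the 80%.

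**Conclusion.** The concern holds. The 80% power in 11.2 does not follow from its own inputs for the test in 11.4. The 25 coincides with a one-sided, one-group normal calculation; that this is how it was obtained is an inference.

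With SD 44% in both groups, normal data and 25 independent cross-reactive clones, the planned test would miss the targeted difference 30% to 59% of the time two-sided, or 20% to 46% one-sided, as comparators go from unlimited down to 25. Gamma data give two-sided misses of 26% to 41% for 250 down to 25 comparators. Higher power is possible if cross-reactive clones vary less, but the plan would have to say so and support it. This should be fixed; it does not affect the primary outcomes.

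**What to change.** In 11.2, recalculate for the test in 11.4. State sidedness, the expected number of strain-specific clones, and an SD for each group from the preliminary data. Replace the 80% with the resulting power or detectable difference, and name the distributional assumption. For example, with 100 comparators, SD 44% in both groups, normal data and a two-sided test, the entry would be 60% power, or a detectable difference of 28 points.

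Name strain-specific clones as the comparator in both sections. If the group SDs differ, specify Welch's test in 11.4. Say whether clones from one donor are treated as independent. Describe 25 as an expected yield, and report the number of distinct donors among the 55.

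The cost is one recalculation and wording in 11.2 and 11.4. The stated power will be less favourable unless the group SDs or the comparator count support a higher figure. No further enrolment is asked for.

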11.3 Planned Interim Analyses (if applicable)

Not Applicable

11.3.1 Safety Review

Not Applicable

11.3.2 Immunogenicity or Efficacy Review

Not Applicable

11.4 Final Analysis Plan

We will use the unpaired Student's t-test to compare the frequencies of strain-specific and broadly cross-reactive clonotypes in the marrow after one year as expressed as a percentage of their frequencies at one month post vaccination. We will also work to develop a multi-phase exponential decay model for plasma cell persistence in the blood and bone marrow over time. We will use ANOVA to evaluate the contributions of antibody specificity (head vs. stem specific; broadly reactive versus strain specific reactivity), affinity for antigen, and level of hypermutation on the observed exponential decay constants of individual clones in each decline phase that we identify through our modeling. This work will be performed in collaboration with the Emory/UGA CEIRS Data Management Team headed by [name] using the approved Data Management Plan for this contract.

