4 STUDY DESIGN

Longitudinal assessment of the participants will be made at every study visit. Assessments will be performed at day 0, 7, 14, 28, 90 and 365 days after immunization as outlined in the following table. Participants will be screened for the presence of both expected reactions to vaccination and for unexpected adverse reactions and enrollment will take place within two weeks post-screening. Subject enrollment will commence with the availability of the seasonal flu vaccine and last for up to 365 days. See table in appendix A. Subjects will be offered the opportunity to participate in the study for up to 3 consecutive years provided eligibility criteria are met each year. Subjects who elect to continue in the study after the first year of participation will be rescreened to verify continued eligibility and re-consented prior to subsequent participation. Re-enrolling subjects will receive new subject identifiers and will count towards the total enrollment number for subsequent years of participation. Enrollment for the next year will begin with the availability of the seasonal flu vaccine. For subjects who elect to re-enroll in the study, the Day 365 visit (\pm 3 month window) would also be the Day 0 visit for the subsequent year.

Due to the COVID-19 pandemic, all non-essential research was halted in mid-March 2020. New enrollments were placed on hold for this study. Follow-up visits were also halted, which impacted the timing of participants' subsequent follow-up visits. For this study, there are participants whose Day 28 and Day 90 visits were impacted. We will request an expansion of the study window for the participants whose visits were impacted. Additional details regarding this are detailed further in the protocol. None of the other visits were impacted.

Dependent upon Emory's guidelines in response to the evolving nature of the pandemic and the prioritization of studies being allowed to re-open, time will be needed to secure the appropriate approvals and clearance to bring research participants back for their missed visits. As such, we would like to request that the missed visit windows for the Day 28 and Day 90 visits be extended for a maximum of up to 180 days, to ensure that ample time is available to bring participants back for their missed visits.

Enrollment for this study ended on March 31, 2020.

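### Section 11.4 analyses clones as if independent in both the t-test and the ANOVA, although clones share donors and re-enrolled people count again under new identifiers

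*Combined protocol and SAP*

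**What the plan says.** Section 11.4 plans an unpaired "t-test to compare the frequencies of strain-specific and broadly cross-reactive clonotypes" in the marrow, each clone's one-year frequency being taken as a percentage of its one-month frequency. The same section continues: "We will use ANOVA to evaluate the contributions of antibody specificity", together with affinity and hypermutation, on the "observed exponential decay constants of individual clones". Specificity there includes broadly reactive against strain-specific. Neither analysis has a term for the donor.

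Section 11.2 sizes the study in clones. It says that "after one year the frequency of the average vaccine-induced clone in the bone marrow is approximately 33% of the frequency observed at one month", with a standard deviation of 44%, and asks for 25 cross-reactive clones to detect 11% against 33%. It expects one such clone in about half of donors, hence 50 donors, with 55 planned.

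Section 11 says "our primary data analytic strategy will be the use of longitudinal data analysis methods", and assigns "general linear mixed models for continuous responses to assess differences among time points".

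Section 4 allows up to three consecutive years of participation: "Re-enrolling subjects will receive new subject identifiers", and each re-enrolment counts towards the total.

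**The concern.** Clones from one donor share the same marrow aspirates, the same visit dates and the same donor biology. Section 7.3 gives the Day 365 visit a window of three months either way, so all of a donor's clones share whatever decay time that donor happened to have. Positive correlation within a donor is therefore plausible, and an unpaired t-test or ordinary ANOVA cannot allow for it.

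Two things are at stake. The p-value may not have its nominal error rate. And the most informative comparison, cross-reactive against strain-specific within the same donor, is not used, although this contrast sets the sample size. Re-enrolment adds a second layer: one person, and possibly one clone tracked in two seasons, can enter as separate independent observations.

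**Working it through.** **The plan's own figure.** The 25 clones reproduce as a one-sided, one-sample calculation against a fixed 33%: (44 × (1.645 + 0.842) / 22)² = 24.7, rounded up to 25. Then 25 / 0.5 = 50 donors, and 50 × 1.1 = 55. The clone is the unit and no donor correlation enters.

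**Inputs.** From 11.2: SD 44, difference 22 (0.5 SD), 50 donors, 25 with one cross-reactive clone. Assumed, because the documents do not give them: m = 5 strain-specific clones in every donor, and donor correlation ρ = 0, 0.1, 0.3 or 0.5. Normal approximation, two-sided 0.05 (11.2 does not state the sidedness).

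**Case A: both types from the same donors, common donor effect.**
- SE assumed by the t-test: 44 × √(1/25 + 1/(50m)) = 44 × √0.044 = 9.23.
- True SE of the same difference: 44 × √(1/25 + (1 + (m−1)ρ)/(50m) − 2ρ/50). At ρ = 0.5: 44 × √(0.04 + 0.012 − 0.02) = 7.87.
- Actual type I error: 2 × (1 − Φ(1.96 × 9.23 / true SE)).
- t-test power: Φ((22 − 1.96 × 9.23) / true SE).
- Random-effect model: generalised least squares with ρ known; power Φ(22 / SE − 1.96).

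| ρ | true SE | t-test type I error | t-test power | model SE | model power |
|---|---|---|---|---|---|
| 0 | 9.23 | 5.0% | 66.4% | 9.23 | 66.4% |
| 0.1 | 8.97 | 4.4% | 66.8% | 8.90 | 69.6% |
| 0.3 | 8.44 | 3.2% | 67.8% | 7.96 | 78.9% |
| 0.5 | 7.87 | 2.2% | 69.0% | 6.77 | 90.2% |

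At ρ = 0.3, with m from 1 to 10, the t-test has 53.6% to 69.9% power and the model 64.3% to 81.6%. The 66.4% at ρ = 0 is below the planned 80% because the named test is two-sample and is taken here as two-sided. That shortfall is a separate matter from clustering.

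**Case B: types from different donors** (strain-specific clones only from the 25 donors without a cross-reactive clone, m = 5). The assumed SE is 44 × √(1/25 + 1/125) = 9.64. The true SE is 44 × √(1/25 + (1 + 4ρ)/125) = 9.96, 10.56 and 11.13 at ρ = 0.1, 0.3 and 0.5. Type I error is 5.8%, 7.4% and 9.0%. If instead only same-type clones within a donor are correlated (50 donors, m = 5), it is 5.4%, 6.3% and 7.1%.

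**Case C: re-enrolment.** Yearly totals of 15, 15, 15 and 10 with a three-year limit allow as few as 15 + 10 = 25 distinct people, since nobody enrolled in year 1 can also be enrolled in year 4. Let f be the share of 50 donor-years that belong to people counted twice, and τ an extra correlation between two records of the same clone. With m = 5:

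variance / 44² = (1 + f(ρ + τ))/25 + (1 + 4ρ + f(5ρ + τ))/250 − (2ρ/50)(1 + f), against 0.044 assumed by the t-test.

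Take ρ = 0.2 and τ = 0.3, both assumed:
- 5 people counted twice (f = 0.2): 0.0426, type I error 4.7%.
- 10 people counted twice (f = 0.4): 0.0461, 5.6%.
- 25 people counted twice (f = 1): 0.06 + 0.0124 − 0.016 = 0.0564, 8.3%.
- 25 people counted twice but no clone recurring (τ = 0): 0.048 + 0.0112 − 0.016 = 0.0432, 4.8%.

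When both types share donors, it is recurring clones, more than recurring people, that push the error rate above 5%.

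**The case against.** **A reader might infer that the t-test is the only formal comparison.** It is not. The ANOVA in 11.4 includes the same broad against strain-specific factor, and Section 11 plans mixed models across time points. The ANOVA shares the flaw, so this widens the point rather than removing it.

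**A reader might infer that 11.4 contradicts Section 11.** The text does not support that. Section 11 gives mixed models to differences among time points, whereas the t-test compares clone types on one derived value per clone. The two sections are unreconciled, not in conflict.

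**A reader might infer that false positives are inflated.** With shared donors and a common donor effect the t-test is conservative. Inflation needs separate donors, type-specific clustering or enough recurring clones, and no re-enrolment rate is given. With 5 or 10 people counted twice the error rate stays near 5% under the assumptions above.

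**The power gain is conditional.** It is about 3 points at a correlation of 0.1 and zero at 0. The model figures treat the correlation as known, so they are a best case. The number of strain-specific clones per donor is also not stated.

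**Linkage is partly implied.** The design schematic treats a later Day 0 as Day 365 or Day 730 of the first year. Section 3.2.3 asks whether the same clones are re-amplified after each vaccination. Section 8.2.1 labels samples with a donor number as well as a study identifier. Whether that number persists across years is not said, and no analysis uses it.

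**Clone tracking is listed as exploratory** in 3.2.3. That stands, but 11.2 sizes the study on it.

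What remains is that neither test has a donor term, and nothing else in the plan supplies one for this contrast.

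**Conclusion.** The point holds. Both analyses in 11.4 treat clones as independent, and the standard error is wrong whenever clones within a person are correlated. The direction depends on the clone mix: at 5 strain-specific clones per donor and correlation 0.5, the assumed SE is 9.23 against a true 7.87 with shared donors, and 9.64 against 11.13 with separate donors. Under shared donors the power given up is about 3, 11 and 21 points at correlations of 0.1, 0.3 and 0.5. The defect is certain from the text. Its size and sign are not, because they rest on a donor correlation, a number of clones per donor and a re-enrolment rate that the documents do not give. The change should be made because it costs little and protects the contrast on which the study is sized.

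**What to change.** In 11.4, state that the clone is the unit of analysis and that people are the clusters. Replace the t-test and the ANOVA with a linear mixed model, or a cluster-robust equivalent. Use clone type as a fixed effect (plus affinity and hypermutation for the decay constants) and a random intercept for person. Robust standard errors around an unchanged difference in means would repair the error rate but would not recover all of the within-donor information.

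Link all re-enrolment identifiers to one person code. Add a clone-within-person effect only where the same clone is tracked in more than one year, since a clone with one persistence value cannot support it; otherwise use only the clone's first tracked year.

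Do not move to a plain log scale. Section 11.2 reports that the cross-reactive clones followed so far were undetectable at one year, and the log of zero is undefined in exactly the group of interest. Either keep the planned percentage scale with robust standard errors, or use a model that treats undetectable clones as censored at the detection limit.

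Cost: analysis wording, a linking code and slightly more analysis work. No new data are needed.
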